6.7.2. Secondary Efficacy Analysis

The secondary endpoints will be analyzed analogously to the primary endpoint, including the treatment of IcEs and missing data.

- Modified Clinical Cure at the Test of Cure visit
- Clinical Clearance at the Test of Cure visit
- Modified Clinical Cure at the End of Treatment visit
- Clinical Clearance at End of Treatment visit
- Clinical Cure at the End of Treatment visit

A stepwise process will be conducted for testing the secondary efficacy endpoints in order to control for multiplicity; refer to [Section 6.1.7.](#)

All secondary efficacy analyses will be presented using the ITT population. Analyses will also be presented in a supportive manner using the PP population. All efficacy data will be included in by-subject listings.

6.7.3. Sensitivity Efficacy Analysis

Sensitivity analyses consist of repeating analyses for the primary and secondary endpoints using the PP population.

6.7.4. Exploratory Efficacy Analysis

Results of the fungal cultures which are taken at designated visits are recorded in the eCRFs and will be presented using descriptive statistics.

6.7.5. Analysis Sites

The study is intended to be conducted in a manner such that a minimum of 5 subjects will be enrolled in each treatment arm for any Investigator site. In the event that there are too few subjects in a treatment arm for a site, then this site's data will be combined with the site with the largest enrollment. If there is a further need to combine data, then the data of the site with the second smallest enrollment will be combined with the site's data which had the second largest enrollment and so on. This process will continue for all sites who did not randomize a minimum of 5 subjects per treatment arm. The process of combining sites that have insufficient subjects per treatment arm will result in redefining sites for the purpose of statistical analyses. These will be referred to as 'analysis sites' in the statistical analyses.

6.8. Safety Evaluation

6.8.1. Extent of Exposure

The extent of exposure to study drug in each treatment group will be summarized by total number of days of exposure, total number of doses, number of missed doses and number and percentage of subjects who are compliant. A subject will be considered compliant with the dosing regimen if the subject applied 80% to 120% of the expected number of doses while enrolled in the study.

Days of exposure = Date of Last Dose – Date of First Dose + 1

Total Number of Doses:

$$2 * (\text{Date of Last Dose} - \text{Date of First Dose} + 1) - (\text{Number of study ear doses missed as collected on the case report form (CRF)}) + (\text{Number of study ear extra doses as collected on the CRF})$$

Total Number of Expected Doses = 28

If a subject discontinues from the study early before the End of Treatment Visit, the number of expected doses will be calculated to the later of the last visit date or date of last dose. If the total number of expected doses exceeds 28 then the total number of expected doses will be set to 28.

Compliance will be calculated as a percentage as 100 times the total number of doses divided by the total number of expected doses.

Extent of exposure summaries will be provided using the Safety population.

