7.11 Treatment Compliance

Subjects or their caregivers (as appropriate) will be given the study drug. Additionally, each bottle of study drug will be weighed by the investigator or designee before dispensing to the subject and at the last visit in which the used bottle is brought to the site.

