10.4.2 Per Protocol Population

The per protocol (PP) population will be a subset of the ITT population and will include all subjects who complete the Test of Cure visit without any major protocol violations. The PP population will exclude subjects from the ITT population that met any of the following criteria:

- Violated the inclusion/exclusion criteria
- Used an interfering concomitant medication
- Did not attend the Test of Cure visit
- Did not attend the End of Treatment visit
- Have not been compliant with the dosing regimen (i.e., subjects must have received 80%-120% of the expected applications of study medication in the study ear during participation in the study)
- Out of visit window at the Test of Cure Visit (-1/+8 days)

Subjects who discontinue from the study due to an adverse event related to study treatment, documented lack of treatment effect, or worsening of condition will be included in the PP population. Prior to breaking the blind, other additional criteria may be added to the list to accommodate for unforeseen events that occurred during the conduct of the trial that result in noteworthy study protocol violations.

All efficacy analyses will be performed using the PP population in a supportive manner.

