4.1. Overall Study Design

This study is a randomized, double-blind, parallel-group study to be conducted at up to 8 study centers in the US. Approximately 110 male or female subjects with otomycosis will receive study drug. Subjects will be randomly assigned in a 1:1 ratio within study site to receive miconazole oil [administered as 5 drops per ear at ~30 mg per drop instilled into the external ear canal of the ear(s) affected by otomycosis] or mineral oil, for 14 days. Both the subject and the investigator as well as study staff will be blinded as to the contents of the study drug.

At Screening/Baseline (Day 1), subjects with positive signs and symptoms of otomycosis and who meet all other eligibility criteria will be entered into the study. A fungal culture of the affected ear(s) will be taken, then debris will be cleaned from the affected ear(s) and the subject will then begin treatment with study drug. The subject or caregiver will instill the first dose of study drug at the site, under supervision of the investigator or site personnel. Adverse events (AEs) will be assessed. The subject will then leave the clinic and continue to administer the study drug twice per day as instructed.

Subjects will continue to administer the study drug twice per day, up through Day 14, following the same instructions as provided at the Screening/Baseline Visit on Day 1. Subjects will then return to the clinic on Day 15 for the End of Treatment Visit, at which time a clinical evaluation of the signs and symptoms of otomycosis will be performed. AEs and concomitant medications will also be assessed, and the subject will return all unused study drug.

Subjects will return to the clinic on Day 22 for the Test of Cure Visit, at which time an assessment of clinical signs and symptoms of otomycosis of the affected ear(s) will be performed (efficacy assessments). AEs and concomitant medications will also be assessed. A urine pregnancy test will be performed in women of childbearing potential.

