6.4.2. Per Protocol (PP) Population

The PP population will be a subset of the ITT population and will include all subjects who complete the Test of Cure visit without any major protocol violations and analyzed according to the treatment each subject actually received. The PP population will include subjects in the ITT population who did not meet any of the following criteria:

- Violated the inclusion/exclusion criteria
- Used an interfering concomitant medication
- Did not attend the Test of Cure visit
- Did not attend the End of Treatment visit
- Have not been compliant with the dosing regimen (i.e., subjects must have received 80% 120% of the expected doses of study medication in the study ear during participation in the study)
- Out of visit window at the Test of Cure Visit (-1/+8 days)
- Missed Test of Cure Visit signs and symptoms

Subjects who discontinue from the study due to an adverse event (AE) related to study treatment, documented lack of treatment effect, or worsening of condition will be included in the PP population. Prior to breaking the blind, other additional criteria may be added to the list to accommodate for unforeseen events that occurred during the conduct of the trial that result in noteworthy study protocol violations.

Efficacy analyses performed using the PP population will be in a supportive manner.

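### The per-protocol retention clause covers leaving the study but not stopping study drug, so subjects who stop drug by Day 11 for a listed reason and stay in follow-up drop out of the only sensitivity analysis

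*SAP*

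**What the plan says.** **Compliance rule.** Protocol 10.4.2 makes dosing compliance a PP criterion: "subjects must have received 80%-120% of the expected applications of study medication in the study ear during participation in the study". SAP 6.4.2 repeats the band in terms of doses in the study ear. SAP 6.8.1 calls a subject compliant "if the subject applied 80% to 120% of the expected number of doses while enrolled in the study".

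**Calculation.** SAP 6.8.1 counts two doses for each day from first to last dose, subtracts "Number of study ear doses missed as collected on the case report form (CRF", and adds extra study-ear doses from the same source. The denominator is fixed: "Total Number of Expected Doses = 28". It is reduced only for a subject who leaves the study before the End of Treatment visit, in which case "the number of expected doses will be calculated to the later of the last visit date or date of last dose", capped at 28.

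**Retention clause.** SAP 6.4.2 keeps some subjects in PP regardless of the criteria. It begins "Subjects who discontinue from the study due to an adverse event (AE) related to study treatment" and goes on to lack of treatment effect and worsening. Protocol 10.4.2 has the same clause.

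**Estimand.** In Protocol 2.3 and SAP 6.7.1 the adverse-event and lack-of-efficacy intercurrent events are stopping study treatment, and a composite strategy counts them as failures.

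**Bottle weights.** Under Treatment Compliance, Protocol 7.11 states that "each bottle of study drug will be weighed by the investigator or designee before dispensing to the subject and at the last visit" to which the used bottle is brought. Table 5 schedules weighing at Day 1 and Day 15. The SAP text available does not mention weights.

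**The concern.** Stopping the drug and leaving the study are different events in this protocol. Section 8.4 records permanent discontinuation of study drug as an action taken for an adverse event. Section 8.5 allows a subject withdrawn from treatment to continue in the study in one circumstance. The estimand is built on stopping treatment, whereas the PP retention clause is built on leaving the study.

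Two subjects with the same drug-related event on the same day can therefore be handled in opposite ways. The one who leaves the study is kept in PP. The one who stays for both visits is judged against all 28 doses and is excluded if the drug was stopped early enough. The exclusion is informative, because it removes subjects whom the primary analysis counts as failures. SAP 6.7.3 defines the sensitivity analyses solely as the PP rerun, so the only check on the primary result is the one affected.

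A lesser concern is that the compliance percentage depends wholly on what is recorded as missed or extra. The protocol describes no diary or other source for those counts, and the one compliance measurement it does describe is not analysed.

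**Working it through.** **1. The plan's own figure.** SAP 4.1 gives the regimen: "Subjects will continue to administer the study drug twice per day, up through Day 14". 2 doses/day × 14 days = 28, which reproduces the stated denominator.

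**2. Drug stopped, subject stays in the study.** The denominator stays at 28. With no missed or extra doses recorded, compliance = 100 × (2 × last dosing day) / 28.

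| Last dosing day | Doses | Compliance | 80% to 120% |
|---|---|---|---|
| 3 | 6 | 21.4% | fails |
| 5 | 10 | 35.7% | fails |
| 11 | 22 | 78.6% | fails |
| 12 | 24 | 85.7% | passes |
| 14 | 28 | 100% | passes |

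The cut falls between Day 11 and Day 12. Recorded misses lower these scores. A recorded extra dose would raise them: one extra with a last dose on Day 11 gives 23/28 = 82.1%.

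**3. Same event, two routes.** Take a related adverse event with last dose on Day 5.
- Leaves the study: kept in PP by the retention clause, whatever the score.
- Attends End of Treatment and Test of Cure: 10/28 = 35.7%, excluded from PP. The retention clause as worded does not apply.

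In the primary ITT analysis both count as failures. The mismatch is clearest for adverse events. For lack of efficacy the estimand also names stopping treatment, but SAP 6.7.1 identifies that event from the recorded reason for leaving the study.

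**4. How many subjects.** The documents give no forecast. In the earlier Phase 3 trial (Protocol Table 3, Randomization Period), 4/88 on miconazole oil and 6/89 on vehicle oil stopped drug because of adverse events. Assuming those rates at 55 per arm:
- miconazole: 4/88 × 55 = 2.5
- control: 6/89 × 55 = 3.7
- together about 6 of 110

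Treatment-emergent events of any kind suspected to be drug-related occurred in 2 + 1 = 3 of 177, or 3/177 × 110 = 1.9 subjects. Only those who stop by Day 11, for a listed reason, and stay in follow-up are affected. Stops for lack of effect not reported as adverse events would add to this, and the documents give no count for them.

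**5. Effect on the PP rates.** Take the planning rates of 35% and 10% and, as an extreme, drop all 2.5 and 3.7 subjects as failures, with no other exclusions:
- miconazole: 0.35 × 55 = 19.25 cures; 19.25 / 52.5 = 36.7%
- control: 0.10 × 55 = 5.5 cures; 5.5 / 51.3 = 10.7%
- difference 26.0 points instead of 25.0

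**6. Bottle weight against dose count.** Protocol 9.1 and 9.1.1 give about 30 mg per drop and 5 drops per ear. Expected use is 28 × 5 × 0.030 g = 4.2 g for one ear and 8.4 g for two.
- Once-daily use with no misses recorded: 14 × 5 × 0.030 = 2.1 g, 50% of expected; SAP score 100%.
- Two drops per dose: 28 × 2 × 0.030 = 1.68 g, 40% of expected; SAP score 100%.
- Six misses that are recorded: (28 − 6)/28 = 78.6%, so the SAP count does detect recorded under-dosing.

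**The case against.** **The impact is small.** ITT is primary, and it already counts subjects who stop treatment for an adverse event as failures. PP is supportive, the numbers in steps 4 and 5 are low, and SAP 6.4.2 does not cross-reference 6.8.1, so the link rests on the shared 80% to 120% band. All of this stands and limits the weight of the point. It does not remove the inconsistency between the retention clause and the estimand.

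**A reader might infer that the formula lets early dropouts into PP as fully compliant.** A subject who stops on Day 3 and has no later visit does score 6/6 = 100%. That does not decide PP membership. The reduced denominator applies only to subjects who leave before End of Treatment. They fail the attendance criteria whatever their score, unless the retention clause keeps them, again whatever their score. This affects the exposure table only.

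**A reader might also infer that under-dosed subjects generally score 100%.** They can, but only if misses go unrecorded or too few drops are used. The case report form is not among the documents, and nothing gives a rate for either.

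**Nor does the SAP contradict the protocol by counting doses.** The protocol's own PP criterion is in applications to the study ear, and neither document sets a weight threshold. Weight would make a poor PP criterion:
- One bottle serves both ears. A subject at 50% in the study ear and 100% in the other uses 2.1 + 4.2 = 6.3 g of 8.4 g, or 75%.
- Drop weight is approximate. If it were 37 mg (an assumption), a fully adherent subject would use 28 × 5 × 0.037 = 5.18 g, which is 123% of 4.2 g.
- The arms receive different oils. If their drop weights differ, exclusion would depend on treatment.

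These objections stand, and they confine weight to a descriptive role.

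**Conclusion.** The retention clause is defective in both documents. It protects subjects who leave the study for a related adverse event, lack of effect or worsening, but not those who stop drug for the same reasons and stay in follow-up. If the last dose is on or before Day 11, the latter score at most 78.6% and leave PP. This assumes that the 6.8.1 calculation is the one used for the PP criterion and that no extra doses are recorded.

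The likely size is a few subjects. About 6 of 110 is a ceiling for adverse-event stops if the earlier trial's rates carry over to this trial, which uses a different control. Even that ceiling moves the PP difference by only about 1 percentage point under the planning rates. The reason to act is that the exclusion removes failures from the only sensitivity analysis and is simple to correct.

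The unused bottle weights are a secondary matter. They justify a descriptive check and do not show that the dose count is wrong. The consequences are confined to the PP analysis and the exposure table, and the primary ITT test is unaffected.

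**What to change.** 1. In Protocol 10.4.2 and SAP 6.4.2, extend the retention clause to subjects who discontinue study treatment or the study for the listed reasons, and state that they count as failures in the PP analysis, as in the primary estimand. Name the eCRF field that identifies stopping drug for lack of effect or worsening, because the SAP currently reads lack of efficacy from the reason for leaving the study.
2. In SAP 6.4.2, cross-reference 6.8.1 for the compliance calculation. In 6.8.1, name the source of the missed and extra dose counts.
3. In SAP 6.8.1, add a descriptive summary by arm of product used (dispensed minus returned weight, including any reserve bottle) against about 4.2 g per treated ear, shown beside the dose-count compliance. Do not use it to define PP.

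The cost is a few sentences before unblinding and one derived variable from weights already scheduled for collection. Treatment, visits and the primary test do not change. The weight summary will be noisy because of approximate drop weight, spillage and lost bottles, and it cannot separate the ears in bilateral subjects. The table should say so.

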6.8.2. Medical History

Medical history results will be presented in a by-subject listing.

6.8.3. Adverse Events

Safety summaries will be conducted using the Safety population.

All adverse events (AEs) occurring during the study will be recorded and classified using terminology from MedDRA.

All reported TEAEs, defined as any AE occurring upon or after administration of the first dose of study drug, will be summarized. Summaries will provide the number of subjects reporting TEAEs, system organ class, preferred term, severity, and relationship to study drug. When summarizing TEAEs by severity or relationship to study drug, each subject will be counted only once within a system organ class or a preferred term using the event with the greatest severity or causality, respectively, within each category. All reported serious AEs (SAEs) will be summarized by the number of subjects reporting the event, system organ class, preferred term, severity, and relationship to study drug.

All information pertaining to AEs noted during the study will be listed by subject and will include a verbatim description of the event as reported by the investigator, as well as the preferred term, system organ class, start date, stop date (if stopped), seriousness, severity, action taken regarding the study drug, corrective treatment, outcome, and relationship to the study drug. In addition, a listing of subjects who prematurely discontinue from the study due to AEs will be provided as well as a listing of subjects who report an SAE.

6.8.4. Physical Examination

Physical examination data will be presented in a by-subject listing.

6.8.5. Pregnancy Testing

Pregnancy testing results will be presented in a by-subject listing.

7. Determination of Sample Size

Approximately 110 subjects (55 per group) provide ~80% power, using a Fisher's Exact test with a 2-sided significance level of .05, to demonstrate a difference between the miconazole oil group and mineral oil group, assuming a response rate of 35% in the miconazole oil group and 10% in the mineral oil group and a chi-square test with alpha of 0.05. These assumptions are consistent with the findings from the first Phase 3 study for the miconazole oil group, and with conservative assumptions for the mineral oil group.

8. Changes from the Protocol in the Planned Analyses

The approach to testing of the secondary endpoints has been added in the SAP.

Intercurrent events are specified in more detail in the SAP.

The protocol erroneously includes the word 'Exact'; the primary endpoint will be tested using a CMH test stratified by analysis site.

No mention of multiplicity strategy toward the testing of secondary endpoints was made in the protocol. The SAP lays out the approach in Section 6.1.7.

9. Revision History

Version	Change Control No.	Effective Date
0	CC-5391	11/05/24
1	CC-5546	02/06/25

Appendix 1: Otomycosis Signs and Symptoms

The signs and symptoms of otomycosis will be assessed according to the scales for pruritus, debris, presence of fungal elements and aural fullness as outlined below.

Pruritus

Score	Category	Description
0	None	No itching; occasional nonspecific itch
1	Mild	Occasional itching, not interfering with daily activities
2	Moderate	Fairly persistent itching, partially tolerated; sleep is not interrupted
3	Severe	Intolerable, constant itching; sleep is interrupted

Debris

Score	Category	Description
0	None/Normal	No debris, normal earwax present
1	Scant	Debris minimally present, but with no notable occlusion of external ear canal
2	Moderate	Debris present with partial occlusion of external ear canal; tympanic membrane can be visualized
3	Heavy	Complete occlusion of ear canal; tympanic membrane cannot be visualized

Presence of Fungal Elements

Score	Category	Description
0	Absent	No fungal elements present on visual inspection with otoscope
1	Present	Fungal elements present on visual inspection with otoscope, such as visualization of white filaments in debris; black, gray, bluish, yellow, or white discharge; white debris with hyphae; or moist white plugs with black debris; or other observations that in the investigator's judgment are indicative of the presence of fungus

Aural Fullness

Score	Category	Description
0	None	Not present
1	Mild	Present but not affecting daily activities
2	Moderate	Present and affecting daily activities but tolerable
3	Severe	Intolerable and severely disrupting daily activities; sleep is interrupted
